#### Missed dose

If a dose is missed, it should be taken as soon as the patient remembers. However, a double dose should not be taken at the same time. In that case, the missed dose should be skipped.

#### *Elderly patients*

In patients 75 years and older, renal function and risk of volume depletion should be taken into account. In patients aged 85 years and older, initiation of JARDIANCE DUO® is not recommended due to the limited therapeutic experience of empagliflozin.

### **8.1.3 Concomitant therapy, Restrictions, And rescue**

Additional drugs are allowed as considered necessary for the patient's welfare to be prescribed at the discretion of the treating physician. It is required, however, to record the details in the eCRF of all concomitant medication administered to the patient during the course of treatment. This includes concomitant therapies started one month prior to JARDIANCE DUO® initiation until the patient completes the final follow-up visit.

#### **8.1.3.1 Restrictions**

- Radiologic studies involving the use of intravascular iodinated contrast materials (for example, intravenous urogram, intravenous cholangiography, angiography, and computed tomography (CT) scans with intravascular contrast materials) -  
Intravascular administration of iodinated contrast media may lead to acute renal failure and has been associated with lactic acidosis in patients receiving metformin. Therefore, in patients with  $eGFR > 60\text{ml/min}/1.73\text{m}^2$ , JARDIANCE DUO® must be discontinued prior to, or at the time of the test and not be reinstated until 48 hours afterwards, and only after renal function has been re-evaluated and has not deteriorated further. In patients with moderate renal impairment ( $eGFR 45-60\text{ml/min}/1.73\text{m}^2$ ), JARDIANCE DUO® must be discontinued 48 hours before administration of iodinated contrast media and not be reinstated until at least 48 hours afterwards, and only after renal function has been re-evaluated and has not deteriorated further.
- In patients with severe infections or severe traumatic systemic disorders, JARDIANCE DUO® should be temporarily suspended, and should not be restarted

until the patient's oral intake has resumed and renal function has been evaluated as normal.

- JARDIANCE DUO® should be temporarily suspended for any surgical procedure (except minor procedures not associated with restricted intake of food and fluids) before 48 hours, and not be reinstated until 48 hours afterwards, after renal function has been evaluated as normal.

Please refer to the current local label for more detailed information ([13.4](#)).

## 8.2 SETTING

As per regulations, enrolled patients will be followed up for 12 or 24 weeks treatment period.

### 8.2.1 Study sites

A total of 600 patients will be enrolled at approximately 20 sites by as many as 20 or more NIS physicians. To minimize the selection bias at the site level, the goal is to have participating centers reflect a balance between general hospitals and clinics for surveillance. The treating physicians will mainly be internists. To minimize the selection bias, consecutive patients from each site who meet inclusion criteria will be enrolled in this study.

As provided in the 『Standards for Re-examination of New Drugs』 of the Ministry of Food and Drug Safety Notification, BI OPU should select study site according to the following requirements;

- ① Equipment/facility, and manpower capable of fully achieving the goal of investigation should be held;
- ② The investigator should have specialized knowledge of the drug subject to investigation and the indication, have completed education/training necessary for performing the investigation, or have practical experience;
- ③ Study site and the investigator should strictly keep confidential the record of subject's personal data
- ④ The investigator should be fully aware of the 『Standards for Re-examination of New Drugs』 and study protocol.

### 8.2.2 Study population

#### 8.2.2.1 Main diagnosis for study entry

Patients diagnosed with type 2 diabetes mellitus in Korea.

JARDIANCE DUO® is indicated as an adjunct to diet and exercise to improve glycaemic control in adult patients with type 2 diabetes mellitus who are appropriate to take a combination of empagliflozin and metformin.

- When the patients never experienced prior treatments and monotherapy would not provide appropriate glycaemic control, or

Proprietary confidential information © 2019 Boehringer Ingelheim International GmbH or one or more of its affiliated companies

- When metformin monotherapy does not provide adequate glycemic control, or
- As add-on therapy to sulphonylurea in patients with insufficient glycemic control despite treatment with metformin in combination with SU, or
- As add-on therapy to pioglitazone in patients with insufficient glycemic control despite treatment with metformin in combination with pioglitazone, or
- As add-on therapy to linagliptin in patients with insufficient glycemic control despite treatment with metformin in combination with linagliptin
- As add-on therapy to insulin in patients with insufficient glycemic control despite treatment with insulin in combination with metformin, or
- As add-on therapy to insulin in combination with sulphonylurea in patients with insufficient glycemic control despite treatment with insulin in combination with metformin plus sulphonylurea, or
- As replacement therapy of empagliflozin plus metformin (Patients switching from separate tablets of empagliflozin (10 mg or 25 mg total daily dose) and metformin to JARDIANCE DUO® should receive the same daily dose of empagliflozin and metformin already being taken.)

#### 8.2.2.2 Inclusion criteria:

- Patients who have started at first time on JARDIANCE DUO® in accordance with the approved label in Korea
- Age  $\geq 19$  years at enrolment
- Patients who have signed on the data release consent form

#### 8.2.2.3 Exclusion criteria:

- Patients with previous exposure to JARDIANCE DUO®
- Hypersensitivity to active ingredients empagliflozin and/or metformin or to any of the excipients
- Moderate (stage 3b) and severe renal failure ( $\text{CrCl} < 45 \text{ ml/min}$  or  $\text{eGFR} < 45 \text{ ml/min/1.73m}^2$ )
- Acute conditions with the potential to alter renal function such as: dehydration, severe infection, cardiovascular collapse (shock), acute myocardial infarction, sepsis
- Type 1 diabetes, acute or chronic metabolic acidosis, including diabetic ketoacidosis with or without coma, history of a ketoacidosis (type 1 diabetes and diabetic ketoacidosis should be treated with insulin).
- Congestive heart failure requiring pharmacologic management, in particular those with unstable or acute congestive heart failure
- Radiologic studies involving the use of intravascular iodinated contrast materials (for example, intravenous urogram, intravenous cholangiography, angiography, and computed tomography (CT) scans with intravascular contrast materials) -  
Intravascular administration of iodinated contrast media may lead to acute renal failure and has been associated with lactic acidosis in patients receiving metformin. Therefore, in patients with  $\text{eGFR} > 60 \text{ ml/min/1.73m}^2$ , JARDIANCE DUO® must be

discontinued prior to, or at the time of the test and not be reinstated until 48 hours afterwards, and only after renal function has been re-evaluated and has not deteriorated further. In patients with moderate renal impairment (eGFR 45-60 ml/min/1.73m^2), JARDIANCE DUO® must be discontinued 48 hours before administration of iodinated contrast media and not be reinstated until at least 48 hours afterwards, and only after renal function has been re-evaluated and has not deteriorated further.

- In patients with severe infections or severe traumatic systemic disorders, JARDIANCE DUO® should be temporarily suspended, and should not be restarted until the patient's oral intake has resumed and renal function has been evaluated as normal.
- JARDIANCE DUO® should be temporarily suspended for any surgical procedure (except minor procedures not associated with restricted intake of food and fluids) before 48 hours, and not be reinstated until 48 hours afterwards, after renal function has been evaluated as normal.
- Patients with malnutrition, starvation, hypostheniam pituitary or adrenal insufficiency
- Impaired hepatic function (since impaired hepatic function has been associated with some cases of lactic acidosis, JARDIANCE DUO® should generally be avoided in patients with clinical or laboratory evidence of hepatic disease), pulmonary infarction, severe respiratory impairment, any condition associated with hypoxemia, excessive alcohol intake, GI disorders such as dehydration, diarrhoea or vomiting
- Pregnant women, women who may be pregnant, nursing women
- Disease which may cause tissue hypoxia (especially acute disease, or worsening of chronic disease) such as: decompensated heart failure, respiratory failure, recent myocardial infarction, shock
- Patients for whom empagliflozin/metformin is contraindicated according local label of JARDIANCE DUO®
- Current participation in other clinical trials

#### 8.2.2.4 Subjects of special investigation

The patient who have signed on the data release consent form, subjects of special investigation (Geriatric(Older than 65 years), Pregnant Women, renal impairment, hepatic impairment and other special population) among the patients who conducted investigation for safety assessment after the administration of JARDIANCE DUO® can be further investigation into cases collected from this study may be taken into account according to the outcome of retrospective analysis.

### 8.2.3 Study visits

#### 8.2.3.1 Screening and run-in periods

This section is not applicable as this is a non-interventional study.

#### 8.2.3.2 Visit 1; Baseline Visit

Upon patient enrolment, the following will be recorded on the patient's eCRF.

- Information on the site (Hospital name, Department, Physician name, Contract date)
- Visit date
- Diagnosis: date of the diagnosis of T2DM, Family history of T2DM
- Inclusion / Exclusion criteria
- Informed consent form: Date of Informed consent
- Demographic data: Age, gender, pregnancy, height, smoking status
- Diabetes mellitus related complication (Retinopathy, Neuropathy, Nephropathy, Vasculopathy, etc.)
- Medical history: Hypertension, Dislipidemia, Coronary artery disease, Stroke, Liver disease, Renal failure, Allergy, Nephropathy, etc. (history of concomitant disease within 6 months)
- Physical examination: body weight, blood pressure in sitting position (SBP, DBP)
- Renal Function: record Serum creatinine, eGFR, urin ACR if blood test result is available (the most recent data prior to baseline)
- Effectiveness endpoints: HbA1c, [REDACTED] (Lab data should be collected within 1 month prior to baseline)
- Concomitant anti-hyperglycemic agent : record any anti-hyperglycemic agents have been taken prior to the baseline visit (within 1 month prior to baseline)
- Concomitant medications: record all medications have been taken at least once since one month prior to the baseline visit.
- Dose of JARDIANCE DUO® given(Daily dose(Dosage/Administration), Start date)

At visit 1, the patient will be requested to contact the treating physician in the event of any adverse events noted after initiating JARDIANCE DUO® treatment.

#### 8.2.3.3 Visit 2; 12 weeks from Visit 1

After 12 weeks from Visit 1, the patients will return for follow-up. The followings will be noted and recorded in the eCRF.

- Visit date
- Physical examination: body weight, blood pressure in sitting position (SBP, DBP)

Proprietary confidential information © 2019 Boehringer Ingelheim International GmbH or one or more of its affiliated companies

- Any change of JARDIANCE DUO® given (Daily dose(Dosage/Administration), Start date, Date of discontinuation or continuation, Action taken, Causality)
- Effectiveness endpoints: HbA1c, [REDACTED]
- Renal Function: record Serum creatinine, eGFR, urine ACR if blood test result is available (The most recent data since last visit, except previously entered data)
- Concomitant anti-hyperglycemic agent including new medications taken since last visit : any change in the concomitant medications (dose and dosing intervals)
- Concomitant medications including new medications taken since last visit : any change in the concomitant medications ( dose and dosing intervals)
- Any changes in laboratory tests if there is any lab result which was clinically significant compared to data before JARDIANCE DUO® therapy (This data is collected on the basis of medical need, i.e. independent of the NIS)
- Any adverse events noted, AESI (Adverse Event of Special interest)
- Study completion status

#### 8.2.3.4 Visit 3; 24 weeks from Visit 1

After 24 weeks from Visit 1, the patients will return for follow-up. The followings will be noted and recorded in the eCRF.

- Visit date
- Physical examination: body weight, blood pressure in sitting position (SBP, DBP)
- Any change of JARDIANCE DUO® given (Daily dose(Dosage/Administration), Start date, Date of discontinuation or continuation, Action taken, Causality)
- Effectiveness endpoints : HbA1c, [REDACTED]
- Renal Function: record Serum creatinine, eGFR, urine ACR if blood test result is available (The most recent data since last visit, except previously entered data)
- Concomitant anti-hyperglycemic agent including new medications taken since last visit : any change in the concomitant medications (dose and dosing intervals)
- Concomitant medications including new medications taken since last visit : any change in the concomitant medications (dose and dosing intervals)
- Any changes in laboratory tests if there is any lab result which was clinically significant compared to data before JARDIANCE DUO® therapy (This data is collected on the basis of medical need, i.e. independent of the NIS)
- Any adverse events noted, AESI (Adverse Event of Special interest)
- Study completion status

#### 8.2.3.5 End of study

- Visit date
- Discontinuation or continuation (if interruption, date of last administration, reason for interruption)

- NIS physician's electronic signature for data integrity

#### 8.2.3.6 Follow-up period

Patients with adverse events noted at the final follow-up visit or upon premature discontinuation of JARDIANCE DUO® will be monitored further until the resolution of those adverse events. Alternatively, those patients will be followed up until the NIS physician and sponsor agree that no further follow-up is necessary.

#### 8.2.4 Study discontinuation

[REDACTED] reserves the right to discontinue the study overall or at a particular study site at any time for the following reasons:

- Emergence of any effectiveness/safety information that could significantly affect continuation of the study
- Violation of applicable local regulations, the NIS protocol, or the contract by a study site or participating physician, disturbing the appropriate conduct of the study.

### 8.3 VARIABLES

#### 8.3.1 Analysis sets

A total of 600 patients will be entered in this study, and each patient will be followed for total three times (baseline, short term 12 weeks follow up, long term 24 weeks follow up). Since T2DM is chronic disease it might be restrictive to collect safety and effectiveness data in short-term (12weeks) period, all patients will be enrolled for long-term (24weeks) surveillance.

##### 8.3.1.1 Number of cases subject who entered the study

This number means the planned number of cases as specified in the contract concluded with the investigator (physician) prior to initiation of the study.

##### 8.3.1.2 Number of cases subject to CRF collection

This number means the number of cases who signed the informed consent form to participate in the study as subject, with a record of taking JARDIANCE DUO® once at least.

##### 8.3.1.3 Number of cases subject to safety evaluation

These include those who signed the informed consent form to participate in this study as subject, took JARDIANCE DUO® once at least, and were followed up by the physician once or more.

Reflecting Ministry of Food & Drug Safety (MFDS) guideline, the cases below shall be excluded from safety analysis (defined below) set in the following order:

- Patients who signed on the data release consent form of JARDIANCE DUO® rPMS prior to the contract date
- Patients administrated JARDIANCE DUO® prior to the contract date

Proprietary confidential information © 2019 Boehringer Ingelheim International GmbH or one or more of its affiliated companies

- c. Patients administrated JARDIANCE DUO® prior to the signed on the data release consent form
- d. Patients who have not taken JARDIANCE DUO®
- e. Follow-up failure: Patients whose safety information can not be obtained due to follow-up Loss
- f. Patients who were prescribed for other indications except indications in the local label

#### 8.3.1.4 Number of cases subject to effectiveness evaluation

These cases include those who signed the informed consent form to participate in this study as subject, visited as per the study schedule, took JARDIANCE DUO®, and were evaluated for the effectiveness.

Reflecting Ministry of Food & Drug Safety (MFDS) guideline, the cases below shall be excluded from effectiveness analysis (defined below) set in the following order:

- a. Patients excluded from safety analysis set listed in section [8.3.1.3](#)
- b. Patients with missing information of assessment of effectiveness set listed in section [8.3.2.2](#) at visit 2, visit 3

### 8.3.2 Endpoints

#### 8.3.2.1 Endpoints of safety

All reported adverse events in patients who take at least one dose of JARDIANCE DUO® will be noted.

[figure not shown]
Endpoints pertaining to safety will be presented as incidence rates of adverse events and will include:

[figure not shown]
- Adverse events
- Unexpected adverse events
- Serious adverse events
- Drug-related adverse events
- Non serious adverse drug reaction
- Adverse event of special interest
- Adverse events leading to discontinuation

#### 8.3.2.2 Endpoints of effectiveness

##### 8.3.2.2.1 Main endpoint

Change from baseline in HbA1c after 12 weeks and/or 24 weeks of treatment

### 8.3.3 Assessment criteria

#### 8.3.3.1 Assessment of safety

[figure not shown]
- Adverse events (event name/ symptoms/ sign/ identify hypoglycemia symptoms)
- Onset date, End date
- Intensity (Mild/ Moderate/ Severe)
- Serious (Serious/ Non-Serious)
- Outcome of the event (Recovered/ Not yet recovered/ Sequela/ Fatal/ Unknown)
- Causality (Certain/ Probable/Likely/ Probable/ Possible/ Unlikely/ Conditional/ Unclassified/ Unassessable/ Unclassifiable)
- Factors other than JARDIANCE DUO® (None/ Concomitant medication/ Concomitant disease/ etc.)
- Action taken with study drug due to AE (Discontinued/ Reduced/ Increased/ Continue/ Discontinued and reintroduced/ Unknown/ Not applicable)
- Recurrence in reintroduced (Recurrence/ No-recurrence/ Unknown/ Not applicable)
- Adverse Event of Special interest (Not applicable/Vaginal moniliasis, vulvovaginitis, balanitis and other genital infection/Increased urination/Urinary tract infection/Volume depletion/ Diabetic Ketoacidosis, Decreased renal function, Hepatic injury defined by the alterations of liver parameters/Lower limb amputation)

- Investigator's comments(if needed)

### 8.3.3.2 Assessment of effectiveness

#### ① HbA1c:

HbA1c should be collected within 1 month prior to baseline and after 12 weeks and 24 weeks of treatment.

### 8.3.4 Items of Investigation

#### 8.3.4.1 Demographic data

For demographic evaluation, following background information of subjects shall be recorded:

- Subject signed date
- Subject study number
- Age
- Gender
- Pregnancy (current status)
- Height
- Body weight
- Smoking status

#### 8.3.4.2 Medical/Surgical history and pre-treatment experience

The medical/surgical history to be collected and the treatment experience prior to administration of this drug includes:

- Date of diagnosis

- Family history of T2DM
- Diabetes mellitus related complication (including but not limited to Retinopathy, Neuropathy, Nephropathy, Vasculopathy, etc)
- Medical history : Hypertension, Dislipidemia, Coronary artery disease, Stroke, Liver disease, Renal failure, Allergy, Nephropathy etc.

#### 8.3.4.3 Concomitant medication

Information on concomitant medication that is to be collected includes:

- Brand name or generic name
- Daily dose
- Unit
- Indication
- Start date
- Date of discontinuation or continuation

#### 8.3.4.4 Drug administration status

Information on the study drug administration status includes:

- Dose
- Unit
- Start date
- Date of discontinuation or continuation

#### 8.3.4.5 Information on the site

Information on the site includes:

- Hospital name
- Department
- Physician name

### 8.4 DATA SOURCES

This study will be carried out in the manner of successive survey that the investigator will be asked to successively write in the case report forms(CRFs) from the subject who was initially administered the drug following the study start date to the requested number of subjects without omission. Prior to initiation of the study, written contract shall be concluded, and this contract shall be concluded with the head of the site or the investigator with his/her consent.

### 8.5 STUDY SIZE

The sample size of 600 patients is based on the requirement of the local regulatory authority (MFDS). As per regulation, long-term surveillance is necessary for the T2DM indication. Since T2DM is chronic disease it might be restrictive to collect safety and effectiveness data

in short-term (12 weeks) period, all patients will be enrolled for long-term (24 weeks) surveillance.

## 8.6 DATA MANAGEMENT

Patients' data will be gathered by eCRF. The data management procedures to ensure the quality of the data are described in detail in the data management plan (DMP) available in TMF. Data management and statistics will be outsourced to a qualified contract research organization (CRO).

## 8.7 DATA ANALYSIS

### 8.7.1 Analysis of demographic data

Demographic data and the health status of subjects for the safety evaluation will be analysed descriptively. For continuous data, mean, standard deviation, minimum value, and maximum value will be described, while for categorical data, frequency will be shown.

Parameters corresponding to demographic data are as mentioned below.

- ① Basic information and disease information
  - Age, gender, pregnancy, body weight, smoking status, diabetes mellitus complications, other medical history, disease period, Family history of T2DM, elderly (Age  $\geq$  65 years), renal impairment and hepatic impairment, allergy, long term use (over 24 weeks)
- ② Medication information
  - Concomitant medication, study drug administration status (total period of drug use, average of daily dose), reason for early interruption, any anti-diabetic agents

To assess the extent of preferential prescribing and the potential for channeling bias, data from the TRAJENTA DUO® (linagliptin/metformin) rPMS will be used as a comparator. The baseline characteristics of patients starting JARDIANCE DUO® for the first time will be compared to the baseline characteristics of patients who started TRAJENTA DUO® for the first time. Proportions and means (SD) of the baseline characteristics will be compared using absolute standardized differences (ASD), where an ASD of at least 10% will be considered a meaningful difference. p-values will also be calculated.

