### 8.7.2 Safety analysis

- ① Among the subjects of safety evaluation, the number of subjects with adverse event incurred and the number of adverse events incurred should be calculated, and the incidence rate of adverse events and the 95% confidence interval should be presented.
- ② The number and percentage of adverse events by type and category should be presented.

- ③ Analysis should be made using Chi-square test or Fisher's Exact test on the adverse event onset status by demographic data of subjects of safety evaluation.
- ④ To estimate any factors that are thought to influence the analyzed incidence rate of adverse events, logistic regression analysis should be conducted, and for statistically significant parameters, the meaning should be described.

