### Collection of AEs

The study design is of non-interventional nature and the study is conducted within the conditions of the approved marketing authorization. Sufficient data from controlled interventional studies are available to support the evidence on the safety and effectiveness of the studied JARDIANCE DUO®. For this reason the following AE collection and reporting requirements have been defined.

All adverse events occurred from the signing date on ICF to 30 days after last administration date of medication need to be collected, documented and reported to the sponsor using the AE reporting form of eCRF ([CRF13.1](#)).

All SAEs, ASAEs and AESIs must be reported within 24 hours of occurrence and via telephone/fax to the Local PV Manager (LPVM) of [REDACTED] using the NIS AE form ([13.2](#)). All non-serious Adverse Reactions associated with JARDIANCE DUO® (empagliflozin/metformin) and pregnancy monitoring forms must be reported within 7 calendar days of occurrence and via telephone/fax to the LPVM of [REDACTED]. If any new or further information to these events is available, a follow-up NIS AE report has to be sent to BI. All SAEs and non-serious AEs must include a causal relationship assessment from the physician.

All ADRs (serious and non-serious), including those persisting after study completion must be followed up until they are resolved, have been sufficiently characterized, or no further information can be obtained.

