5.5 Other Statistical Considerations

The analysis will be conducted in consideration of the following matters, and if separate considerations are needed depending on the analysis item, the contents will be described in the relevant item of '7.1 Derivation'.

- The standard for converting Day into Month or Year is as follows: 1 month = 30.4375 days, 1 year = 365.25 days
- For all data analyses, the test statistic is a two-sided test, and the statistical significance level is based on 0.05.
- When calculating percentages from categorical demographics and baseline data, the denominator is defined as the sum of the number of subjects in each category. However, for analysis by detailed medical history/medication type, the denominator is defined as the number of subjects with medical history/medication.
- When calculating percentages of the incidence of adverse events and valid/invalid by demographics and baseline data, the denominator is defined as the number of subjects in each category. However, upon analyzing by detailed medical history/medication type, the denominator is defined as the number of subjects with medical history/medication in each category.
- When calculating the percentage of the incidence for each type of adverse event, the denominator for analyzing the safety analysis set is defined as the number of subjects in the safety analysis set. However, in the analysis of subjects excluded from safety evaluation, the denominator is defined as the number of subjects excluding those who were investigated in duplicate, those who did not receive this drug, or those who did not undergo follow-up for safety.

- In categorical data, if the cells with an expected frequency of less than 5 are more than 20% of all cells in the between group test, Fisher's exact test is used for analysis instead of the Chi-square test.
- For the confidence interval, a 95% two-sided confidence interval is calculated by applying the exact confidence interval method.
- If the total number of adverse events is 10 or less, the analysis of the incidence of adverse events by demographics and baseline data can be replaced with the list of adverse events.
- Multiple logistic regression analysis is not performed when there are two or less variables that show significant differences in the analysis of the incidence of adverse events by demographics and baseline data.

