6.3 Demographics

- Continuous Data:

- Birth of year
- Body weight

- Categorical Data:

- Gender
- Birth of year
- Smoking status
- Early termination and reasons

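### Post-baseline items listed as demographic data (24-week use, total period of use, early interruption) are tested as factors for adverse events, so significant factors can appear with no true risk factor

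*Protocol*

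**What the plan says.** Protocol 8.7.1 sets out which parameters count as demographic data. One list, of basic and disease information, includes "renal impairment and hepatic impairment, allergy, long term use (over 24 weeks"). The other, on medication, includes "study drug administration status (total period of drug use, average of daily dose), reason for early interruption".

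Protocol 8.7.2 uses that category for testing. Item 3 asks for a chi-square test or Fisher's "Exact test on the adverse event onset status by demographic data of subjects of safety evaluation". Item 4 asks for logistic regression to find factors influencing AE incidence and says that "for statistically significant parameters, the meaning should be described".

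Other passages show that these items are post-baseline:

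- Protocol 8.2.3.5 records at end of study "Discontinuation or continuation (if interruption, date of last administration, reason for interruption").
- Protocol 10.2 ties the AE window to duration of use: "All adverse events occurred from the signing date on ICF to 30 days after last administration date of medication need to be collected".

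The visible SAP does not restrict the tests to baseline values:

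- SAP 6.3 lists "Early termination and reasons" under Demographics.
- SAP 5.5 makes the multiple logistic model depend on the number of "variables that show significant differences in the analysis of the incidence of adverse events by demographics and baseline data"; it runs only with three or more.
- SAP 7.2 gives categories for 24-week follow-up, total administration period and discontinuation.
- SAP 6.5 sets a window of one month before baseline for concomitant drugs. No similar limit is visible for the items above.

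**The concern.** A test of AE occurrence by a patient characteristic supports a statement about risk only if the AE could not have changed that characteristic. Duration of use and early termination fail this condition in two ways.

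- **Reverse causation.** An AE that leads to stopping moves the patient into the short-use group, which raises AE incidence there.
- **Time at risk.** A patient who stops early for another reason is observed for a shorter time, which lowers AE incidence in the short-use group.

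The two biases oppose each other. Neither the size nor the sign of the association can therefore be read as a risk factor. If reason for interruption is tested level by level, the level for stopping because of an AE has 100% AE incidence by definition.

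At stake is the factor analysis, the part of the safety analysis whose significant results the protocol wants interpreted. Long use could be reported as protective or as harmful purely because of why and when patients stop. Spurious hits also count towards the three significant variables that trigger the multiple logistic model.

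**Working it through.** **Inputs from the documents.** N = 600, single arm (Protocol 8.5). Follow-up is 24 weeks, or 168 days (Protocol 8.3.1). Tests are two-sided at 0.05, with Fisher's test when more than 20% of cells have an expected count below 5 (SAP 5.5). AEs are collected to 30 days after last dose (Protocol 10.2). The sample size is a regulatory requirement and has no derivation to reproduce. The only plan figure to check is the 5% level.

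**Assumptions, because the documents give no rates.** No variable affects AE risk. The AE hazard is constant, with 24-week risk *p*. A share *d* stops for other reasons at uniform times. A first AE on drug stops treatment with probability *c*. AEs are counted to the earlier of last dose + 30 days and day 168.

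**Expected incidence, base case *p* = 0.20, *d* = 0.15, *c* = 0.20.**

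- Hazard: λ = −ln(1 − *p*)/168 = 0.22314/168 = 0.0013282 per day.
- Counted AE risk for a patient who stops for another reason: *q* = [138 − (e^(−30λ) − e^(−168λ))/λ + 30*p*]/168 = [138 − 0.16094/0.0013282 + 6]/168 = 22.83/168 = 0.136.
- At least 24 weeks: *p*(1 − *c*)/(1 − *pc*) = 0.16/0.96 = 16.7%.
- Below 24 weeks: [(1 − *d*)*pc* + *dq*]/[(1 − *d*)*pc* + *d*] = (0.0340 + 0.0204)/(0.0340 + 0.15) = 0.0544/0.184 = 29.6%.
- Odds ratio: (0.296/0.704)/(0.167/0.833) = 2.1.
- Patients stopped by an AE: 600 × (0.85 × 0.04 + 0.15 × 0.20 × 0.104) = 20.4 + 1.9, about 22. Here 0.104 = 1 − 0.2/0.22314 is the chance that the AE precedes a uniform stopping time.

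The same formulas for other rates, with the simulated share of studies in which the 24-week test is significant:

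| AE risk | Other stopping | AEs that stop drug | AE % <24 wk | AE % ≥24 wk | Odds ratio | Significant |
|---|---|---|---|---|---|---|
| 20% | 15% | 20% | 29.6 | 16.7 | 2.1 | 85% |
| 20% | 15% | 10% | 22.4 | 18.4 | 1.3 | 17% |
| 20% | 15% | 0% | 13.6 | 20.0 | 0.63 | 28–29% |
| 20% | 25% | 10% | 18.5 | 18.4 | 1.0 | 5–6% |

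**Further simulation results.**

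- *Other codings, base case.* Total period in three classes (<12, 12 to <24, ≥24 weeks) is significant in 80% of studies, and early termination Yes/No in 85%.
- *Visit timing.* If 5/10/20/30/50% of completers are seen before day 168 and so fall among short users, the 24-week figure drops to 77/70/51/40/22% and the three-class figure to 69/62/52/47/38%. Early termination Yes/No does not depend on visit timing (84–86%).
- *Range.* For AE risk 10–30%, other stopping 10–25% and AE-driven stopping 10–30%, the 24-week and Yes/No tests are significant in about 4% to 100% of studies (odds ratio 0.98–4.5).
- *Sign.* With no AE-driven stopping the odds ratio is 0.61–0.68, significant in 8–62%.
- *AE window.* If completers also stop at week 24 and have AEs counted for 30 more days, the base case falls to about 60% (odds ratio 1.7). With no AE-driven stopping the reversed result rises from 28–29% to 51%.
- *Reason by level.* Coded as completed, AE or other, it is significant in 98–100%. By Fisher's test, 2 patients in 600 who stopped for an AE give p = 0.0099 at 10% AE incidence and p = 0.040 at 20%; 3 patients give p = 0.027 at 30%. The documents do not state this coding.
- *Control.* A binary variable fixed at first dose, tested in the same data, is significant in 5%.

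A separate simulation, with exponential times for other stopping (10% or 20%), gave 5.6–100% for the 24-week test and 4.3–5.9% for baseline variables.

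**The case against.** The strongest counter-argument is that the governing text may not be visible. SAP 6.8 points to a section 6.8.3 that is not in the available text and is probably where the factor list sits. SAP 5.5 calls the tested items demographics and baseline data. SAP 6.7 puts duration and dose under treatment status, and SAP 6.8.2 gives AE incidence by <24 and ≥24 weeks without naming a test. Protocol 8.7.1 itself says its data are analysed descriptively. This limits the SAP side of the point: only early termination visibly sits under Demographics there, so for duration, 24-week use and dose the point rests on the protocol. It does not remove the protocol wording, because 8.7.2 applies tests to a category that 8.7.1 has just defined.

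Second, every rate is assumed and the result is sensitive to them. Halving AE-driven stopping takes the base case from 85% to 17%. The 85% is therefore an illustration and not a forecast. What stands is that false factors can arise, in either direction.

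Third, a statistician could describe the meaning of a significant result by saying that stopping followed the AE, and a level named for AEs would mislead few readers. That is fair for reason by level, but much less so for 24-week use or total period, where the cause is hidden. Protocol 8.9.1 and 8.9.3 acknowledge informative censoring and confounding, but neither changes the tests.

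Fourth, average daily dose was not simulated and is probably only weakly affected. That also stands.

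**Conclusion.** The concern holds. Read together, Protocol 8.7.1 and 8.7.2 test AE occurrence against items that an AE can itself change, and no visible passage limits the tests to baseline values. With no true risk factor, the 24-week and early-termination tests can be significant in anything from about 4% to 100% of studies of 600 patients. The direction depends on how often AEs stop the drug. Variables fixed at first dose keep the nominal 5%.

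The size rests on assumed AE, stopping and visit-timing rates, and the SAP's own factor list could not be read. Overall AE incidence and incidence by system organ class and preferred term, with exact confidence intervals, are unaffected, and the study has no decision rule. This should be fixed, but it does not threaten the main safety estimates. Confidence is medium.

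**What to change.** In Protocol 8.7.2 items 3 and 4, and in the matching SAP factor analysis, limit AE tests and the logistic model to variables fixed at or before first dose: age, sex, weight, smoking, disease duration, family history, complications, medical history, allergy, renal and hepatic impairment, prior antidiabetic drugs and concomitant drugs in the SAP 6.5 pre-baseline window, and starting dose. Apply the same limit to the count of significant variables in SAP 5.5.

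Report 24-week use, total period of use, average daily dose, and early termination with reasons descriptively, without tests or a risk-factor reading. If duration is of interest, tabulate first AE onset by period (weeks 0–12, >12–24, >24), with patients at risk or patient-time as denominator.

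The cost is wording in both documents, notification of the protocol change to MFDS (Protocol 8.10), and one optional table. No new data are needed, since onset, dosing and visit dates are already collected. The post-baseline comparisons lose their p-values. The MFDS guideline could not be consulted; if it asks for AE tables by these items, they can stay as descriptive tables.
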